We plan to enroll up to 3 leaders/staff and up to 15 youth/YA participants working with one organization.

Phase 2

We plan to enroll up to 3 leaders/staff from each of four organizations (two of the organizations will receive the intervention, two will be control groups). For each organization randomized to receive the intervention, we will also enroll up to 60 youth/YA participants.

Total

Across both phases, we plan to enroll up to 15 organizational leaders/staff and up to 120 youth/YA participants, for a total possible N of up to 135 people.

Interventions and Interactions

All interviews will be conducted by study staff and may occur in-person, by telephone, or by video call, based on logistical considerations and participant preference. Interviews will be audio-recorded for transcription purposes. Interviews may be conducted individually or in groups and should last 30 minutes, and no more than 60 minutes. All surveys will be completed electronically via REDCap and should last around 20 minutes. Study staff will also periodically conduct and audio-record problem-solving check-ins with organizational leaders/staff.

Phase 1

For organizations, feasibility data will be collected of organization leaders/staff who are involved in implementing the YE strategy, via one survey and one interview per leader/staff. The organization will be paid \$250 for their participation in the open trial. This token of appreciation is for the leaders/staff's time spent engaging with study staff and providing feasibility data through interviews and written feedback.

Study staff will administer (or we will train organization staff to administer) surveys via REDCap to assess their impressions of their YE work as well as constructs such as self-efficacy, connection, and knowledge about substances. Each survey should require no more than 30 minutes each and youth/YA participants will be paid a \$15 gift card (e.g., Amazon) upon completion. The YE strategy manual will be revised based on information learned from the feasibility data.

The timeframe for this phase will be 6-12 months.

Phase 2

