We will follow similar interview and survey data collection procedures as in Phase 1, with adaptations as needed based on participant feedback. However, only organizations randomized to treatment will include youth/YA participants. Youth/YA survey data will be collected at the start of their participation in the YE strategy (pre-YE) and 6 months later (post-YE). At the post-YE we will interview a subset of interested YE group participants to qualitatively assess their experiences and to identify, in their own voices, what aspects of YE emerge as important to youth development and their health-related decision-making. Youth/YAs will be paid \$10 for the pre-YE survey, \$15 for the post-YE survey, and \$25 for an interview (for a subset of youth/YA), for a maximum total of \$50 in gift cards.

The timeframe for this phase will be 12-18 months.

Outcome Measure(s)

Phase 1

For organizations, information collected from staff via surveys and interviews will include: the facilitators and barriers of incorporating YE into prevention, the acceptability

of the strategy, evaluation of the support and resources available and what else would be needed to successfully implement YE, and perceived usefulness for YAs and the organization.

For the youth/YAs, information collected via surveys will include: skills (e.g., leadership, communication) and attitudes (e.g., self-efficacy, social connectedness, self-confidence, meaningful social role) as well as knowledge and views of substance misuse. In interviews, we will ask youth/YAs about the facilitators and barriers of participating in the prevention effort, the acceptability of the YE strategy, evaluation of the experience working with the community organization, and likelihood of continued participation. For both organizations and individuals, feasibility data will be collected regarding retention of youth/YAs in the prevention work.

Phase 2

For organizations, information collected from staff via surveys and interviews will include: perceived value added to prevention programming; retention of YAs in prevention programming; reach of prevention efforts in the community; perceived usefulness of YE to the organization, the YAs, and to the community; and perceived effectiveness of incorporating YE into prevention efforts.

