For the youth/YAs, information collected will include: skills (e.g., leadership, communication) and attitudes (e.g., self-efficacy, social connectedness, self-confidence, meaningful social role) as well as knowledge and views of substance misuse. The outcomes will be measured through self-reported surveys. These will serve as benchmarks that the YE intervention has the intended effect at the individual (psychosocial) level.

Analytical Plan

Phase 1 will examine descriptive statistics collected via surveys (from organizational staff and youth/YAs) and exploratory themes collected from interviews.

Phase 2 analyses will examine the effects of the YE prevention strategy on *organization* level outcomes such as perceived value of YE added to prevention programming, and secondarily, on *individual* level skills and attitudes of the youth/YAs involved in the YE. We hypothesize that YE-involved youth/YAs will show gains in skills (leadership, communication) and attitudes (self-efficacy, social connectedness, self-confidence, meaningful social role) as well as more knowledge and less favorable views of opioid misuse (compared to “pre” measures). These data will be used to estimate the effect sizes needed to power a larger study. These data will serve as additional information about the recruitment, feasibility, retention, fidelity and acceptability of the intervention. Comparison between groups will be done using chi square tests for proportions, and t-tests or ANOVA procedures for continuous variables. Regression analysis will be performed to identify independent outcome predictors. Other inferential statistical analysis will be conducted as appropriate.

Human Subjects Protection

Subject Recruitment Methods

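### Does the Phase 2 youth pre/post hypothesis need a named paired analysis and an effect-size definition in the plan?

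*Combined protocol and SAP*

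**What the plan says.** In the Analytical Plan, the Phase 2 youth hypothesis reads "We hypothesize that YE-involved youth/YAs will show gains in skills (leadership, communication) and attitudes", followed by more knowledge and "less favorable views of opioid misuse (compared to “pre” measures". The comparator is therefore the youths' own earlier scores. The next sentence gives the use: "These data will be used to estimate the effect sizes needed to power a larger study".

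The tests follow: "Comparison between groups will be done using chi square tests for proportions, and t-tests or ANOVA procedures for continuous variables". Regression is reserved for finding predictors of outcome, and the paragraph closes with "Other inferential statistical analysis will be conducted as appropriate". Youth outcomes are described as secondary to the organization-level outcomes.

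Three other places bear on the point:

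- Interventions and Interactions, Phase 2: "only organizations randomized to treatment will include youth/YA participants", and "Youth/YA survey data will be collected at the start of their participation in the YE strategy (pre-YE) and 6 months later (post-YE".
- Sample size, Phase 2: "For each organization randomized to receive the intervention, we will also enroll up to 60 youth/YA participants".
- Confidentiality and Privacy: identifiers are collected on the survey so that each youth's two surveys can be matched.

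The documents give no alpha, power, effect size, SD, pre/post correlation or dropout rate for the youth outcomes.

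**The concern.** The only tests named are tied to a comparison between groups, yet control organizations have no youth participants. Read literally, the youth hypothesis has no analysis of its own. No paired t-test, repeated-measures ANOVA, mixed model or change score appears anywhere.

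Naming a paired test would not close the matter either. A pre/post gain can be divided by the SD of scores or by the SD of change, and the two agree only when the pre/post correlation is 0.5 (with equal SDs). Since the pilot is meant to supply effect sizes for a larger study, a number whose denominator is unknown could mislead whoever plans that study. A further worry is that an analyst might treat linked surveys as independent samples and lose precision.

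**Working it through.** The plan has no figure on this point to reproduce, so the check has two parts: what the text implies, and how much the unstated convention could matter.

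**1. Which analysis the text implies.** Set the sections side by side.

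- Two survey times, 6 months apart, on the same youths (Interventions and Interactions).
- The comparator is the pre measure (Analytical Plan).
- Identifiers are gathered for the express purpose of matching the two surveys (Confidentiality and Privacy).
- Only treatment organizations enroll youth, so the between-groups sentence naturally refers to the organization comparison.
- t-tests and ANOVA have paired and repeated-measures forms, and the closing sentence leaves room for others.

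All of this points to a within-person comparison, and nothing prescribes an independent-samples test for youth. Such a test would inflate the standard error by 1/√(1 − r), that is 1.20, 1.41 and 1.83 at r = 0.3, 0.5 and 0.7. The error would be conservative, and it belongs to an analysis the plan does not state.

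**2. Size of the standardizer question.** Assumptions, none from the documents: SD 1 at each survey, true gain 0.30, r = 0.3, 0.5 or 0.7.

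- SD of change = √(2(1 − r))
- Effect on the SD-of-change scale = 0.30 / √(2(1 − r))
- n per arm for a later two-arm trial (80% power, two-sided 5%) = 2(1.960 + 0.842)² / d², rounded up

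| r | SD of change | Effect, score SD | Effect, SD of change | n per arm, score SD | n per arm, SD of change |
|---|---|---|---|---|---|
| 0.3 | 1.183 | 0.30 | 0.254 | 175 | 245 |
| 0.5 | 1.000 | 0.30 | 0.300 | 175 | 175 |
| 0.7 | 0.775 | 0.30 | 0.387 | 175 | 105 |

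The n ratio is 2(1 − r) = 1.40, 1.00, 0.60. Neither column is wrong in itself. A two-arm comparison of follow-up scores alone has variance 2/n, which gives 175. A two-arm comparison of change scores has variance 2 × 2(1 − r)/n, which gives 245, 175 or 105. An error arises only if the planner of the later trial pairs one SD with the other analysis.

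**3. Can a reader convert?** Yes, from ordinary paired reporting:

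- r = (s₁² + s₂² − s_d²) / (2 s₁ s₂), where s₁ and s₂ are the two survey SDs and s_d is the SD of change.
- s_d = h√n / t, where h is the half-width of the 95% interval for the mean change.

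Take 105 pairs: the overall cap of 120 youth less 15 in Phase 1, assuming no dropout. The 2 × 60 = 120 that the Phase 2 limits allow would change nothing here. At r = 0.7 the half-width is 0.150. Then s_d = 0.150 × 10.247 / 1.983 = 0.775, and r = (1 + 1 − 0.601)/2 = 0.70. At r = 0.3 the half-width is 0.229, so s_d = 1.183 and r = (2 − 1.400)/2 = 0.30. The correlation is recovered without being reported.

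**The case for a change.** The best case for a change is that effect sizes for the larger study are a declared product of the pilot, the plan gives no metric for them, and one sentence would settle it at no cost to participants. If a report gave only a bare standardized number, a reader could not tell which SD lay beneath it, and the direction of any error would depend on an unknown r.

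The omission is real and the arithmetic is right. The harm, though, needs several further steps. Effect size must be read as a standardized index, although a mean change with its SD would satisfy the plan's words. The report must then omit the SDs and the interval, which nothing in the plan proposes. The later planners, who could draw on linked data that the team keeps, must then apply the wrong SD to their design. The reference to these data may also cover Phase 2 as a whole, since the following sentence uses the same words for recruitment, fidelity and acceptability.

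The suggested sentence would not settle the planning question by itself either. A paired t-test and a mixed model can differ when follow-up surveys are missing. The lack of control youth and the clustering of youth in two organizations also bear on the planning value of a pre/post gain. Those are separate matters that naming an SD does not touch.

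**Conclusion.** No change to the plan is called for. The Analytical Plan is silent on the paired form and on the standardizer, but the design makes the within-person comparison plain and no stated test or figure is wrong. Following the plan as written, with the linked surveys it provides for, gives sound youth results.

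What remains is a reporting convention for secondary outcomes in a small pilot. At the assumed correlations of 0.3 to 0.7, the same 0.30 SD gain could be quoted as 0.25 to 0.39, with no difference at 0.5. That range reflects two valid scales, and either can be turned into the other from routine summaries or from the retained data. The choice can be made when results are written up, because nothing about data collection depends on it. This rests on two assumptions: that analysts use the linkage the plan sets up, and that they report SDs and an interval for the change, as paired analyses ordinarily do.

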Phase 2: To evaluate the preliminary effectiveness of YE as a prevention strategy for opioid misuse in a small pilot randomized control trial (RCT). This pilot study will examine the effects of the YE prevention strategy on (a) organization-level outcomes, such as perceived value added to prevention programming and (b) individual-level outcomes such as personal skills and attitudes as well as knowledge and attitudes about substances including opioids.

Methods and Measures

Design

Phase 1 will consist of a small open trial. We will implement an organization-level YE prevention strategy by systematically incorporating YE into prevention efforts in a community setting. We will assess feasibility, acceptability, and usability to the community organization and to the young people with whom it works. The results of Phase 1 will inform Phase 2.

Phase 2 will consist of a small pilot RCT. Four prevention organizations will be randomized either to include YE in prevention efforts (treatment) or not (control). We will attempt to

match the treatment and control groups on relevant characteristics such as geographic location (e.g., urban, rural), population served (e.g., church-based, school-based), and/or prior YE involvement.

Setting

This study will be conducted with community-based prevention organizations.

Subjects selection criteria

Participants will consist of leaders or staff from community-based prevention organizations, as well as youth/YAs who are engaged as volunteers with the organization's opioid misuse prevention efforts. These youth/YAs will consist of a community sample, not clients at risk or in recovery for substance misuse. The below criteria apply to both Phase 1 and 2.

Inclusion Criteria:

Organizational leaders/staff

- Leaders or staff of community-based prevention organizations
- Organizations are youth/YA-serving and focused on opioid misuse prevention
- Organizations demonstrate readiness, interest, need, and resources to invest in YE as part of prevention
- Leaders or staff are or would be involved in implementing YE strategy at the organization
- Leaders or staff are able to speak and read English fluently

Youth/YA participants involved with organizations

- Adolescents and YAs age 11 – 29
- Interested in participating in YE with the community organization
- Able to speak and read English fluently

Exclusion criteria:

- Organizations already incorporating a high level of YE in their prevention work

Sample size

Phase 1

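### The Phase 2 youth data are a one-arm pre-post change and cannot supply a between-arm effect size for a larger controlled study

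*Combined protocol and SAP*

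**What the plan says.** The Sample size section sets the Phase 2 numbers. For staff: "We plan to enroll up to 3 leaders/staff from each of four organizations", where "two of the organizations will receive the intervention, two will be control groups". For youth: "For each organization randomized to receive the intervention, we will also enroll up to 60 youth/YA participants". The Phase 2 part of Interventions and Interactions adds that "only organizations randomized to treatment will include youth/YA participants", and has them surveyed when they start and again six months later.

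In the Analytical Plan the youth hypothesis predicts gains in skills and attitudes, more knowledge, and "less favorable views of opioid misuse (compared to “pre” measures". The comparator is thus each participant's own baseline. The next sentence is the one at issue: "These data will be used to estimate the effect sizes needed to power a larger study". The plan then adds feasibility-type uses such as recruitment, retention and fidelity, and lists standard two-group tests and regression.

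The document does not say which outcomes the sentence covers or what design the larger study will have. It mentions no confidence intervals and no allowance for organization. It gives no step for turning a pre-post change into a between-arm effect, and no warning against doing so.

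**The concern.** A larger controlled study is sized on the difference between what happens with YE and what happens without it. The Phase 2 youth data contain only the first half of that difference. Over six months, scores for leadership, self-efficacy, connectedness or views on opioids can move for other reasons: maturation, answering the same survey twice, regression to the mean, or loss of less engaged participants before the second survey. Participants are aged 11 to 29, and the Background section itself presents these years as a time of social development, so background change is plausible. Nothing in the document gives its size or sign.

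What is at stake is the size of the later study. If the one-arm change is taken as the planning effect, that study may be too small or too large, and the pilot cannot show which. The conduct of this trial and its participants are not affected.

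**Working it through.** **Inputs from the document.** Four organizations, two per arm. Up to 3 staff in each, so at most 6 against 6. Up to 60 youth in each of two treatment organizations, so at most 120, and none in control organizations. Two youth surveys, six months apart. The document gives no effect size, SD, ICC, power or significance level, so there is no figure of its own to reproduce.

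**Assumptions (none from the document).** Two-sided 5% level, 80% power, outcome SD of 1, observed youth gain of 0.30 SD, background change B between −0.15 and 0.15 SD. For the intervals: pre-post correlation r of 0.5 to 0.7, ICC of youth change 0 to 0.10, m = 40 to 60 youth followed per organization, staff ICC 0.01 to 0.20.

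**Step 1: what the youth data estimate.** Let T be the YE effect and B the mean change that would have occurred without YE. The observed change estimates T + B, whereas a controlled study targets T. Only youth without YE could estimate B, and there are none. The two parts therefore cannot be separated at any youth sample size, and the observed change is unbiased for T only if B = 0.

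**Step 2: consequence if T + B is used as T.** The number per arm is 2(1.960 + 0.842)²/d² = 15.70/d², rounded up. At d = 0.30 this gives 175. Power with 175 per arm is Φ(d√(175/2) − 1.960) = Φ(9.354d − 1.960). The true d is 0.30 − B.

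| B (SD) | true d | needed per arm | power with 175 per arm |
|---|---|---|---|
| −0.15 | 0.45 | 78 | 99% |
| −0.10 | 0.40 | 99 | 96% |
| 0 | 0.30 | 175 | 80% |
| 0.10 | 0.20 | 393 | 46% |
| 0.15 | 0.15 | 698 | 29% |

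These counts are before any inflation for clustering.

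**Step 3: would a youth interval help?** The variance of the change is 2(1 − r), and the variance of an organization mean is v = 2(1 − r) × [ICC + (1 − ICC)/m]. With two organizations there is 1 degree of freedom (t = 12.71), and the average half-width is 12.71 × 0.798 × √(v/2).
- Best case (r = 0.7, ICC 0, m = 60): v = 0.010, half-width 0.72 SD.
- Worst case (r = 0.5, ICC 0.10, m = 40): v = 0.1225, half-width 2.51 SD.

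Ignoring organization, the half-width is 1.96 × √(2(1 − r))/√(2m), or 0.14 to 0.22 SD in the same two cases, but that leaves out variation between organizations. Neither interval removes B.

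**Step 4: staff, if the sentence covers them.** With 3 staff per organization, v = ICC + (1 − ICC)/3, which is 0.340 at ICC 0.01 and 0.467 at 0.20. The standard error of a 2 against 2 difference is √(v/2 + v/2) = √v, or 0.583 to 0.683. With 2 degrees of freedom t = 4.30, and the estimated SD averages √π/2 = 0.886 of the true one. The average 95% half-width is therefore 4.30 × 0.886 × √v = 2.2 to 2.6 SD. For scale, a true difference of 0.5 SD would come out with the wrong sign with probability Φ(−0.5/√v), or 20% to 23%.

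**The case against.** The strongest reply is that the plan does not commit the misuse. It does not say that a point estimate will be plugged in or that a pre-post change will be read as a between-arm effect, and it does not say that the larger study will be controlled. It calls Phase 2 a small pilot of preliminary effectiveness, states openly that youth are compared with their own baseline, and treats the youth outcomes as benchmarks. This stands in part. A reader might infer that the planning figure *would* be wrong. The documents do not support that: with no background change there is no bias, and another uncontrolled pre-post study could use the figure as it is. What remains is that the sentence assigns the use without limit, that Phase 2 is itself a randomized trial with planned between-group comparisons, and that the pilot label does not withdraw the use.

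It can also be said that, by position, the sentence refers to the youth data and not to staff. That is a fair reading, so the staff part is conditional here. A reader might go further and infer that staff items on YE itself ("perceived usefulness of YE to the organization, the YAs, and to the community; and perceived effectiveness of incorporating YE into prevention efforts") have no counterpart in control organizations. The documents do not settle this: only organizations with a high level of YE are excluded, so controls may have some experience to rate.

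Finally, a reader might conclude that no pilot effect may ever inform planning, or that the larger study must use a minimum important difference and outside ICCs. Statisticians differ on those choices, and they belong to that study's own protocol.

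**Conclusion.** Wrong as written, on the youth part. The design cannot yield a youth between-arm effect size at any sample size, and no passage limits the stated use. That conclusion needs none of the assumed values; it needs only that the larger study be controlled. The size of any error is unknown. The calculated range, from 29% to 99% true power for a study planned at 80%, illustrates background change of 0.15 to −0.15 SD around an assumed 0.30 SD gain and is not an estimate.

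The staff part is secondary. That contrast is randomized, but under the assumed ICCs it is too imprecise for its point estimate alone to size a study. None of this says that the pilot is too small for its feasibility aims.

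**What to change.** Replace the sentence in the Analytical Plan with:

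> Youth pre-post changes will be reported with 95% confidence intervals as within-group changes and will not be used as between-arm effect sizes for a larger controlled study. The intervals will be described as not capturing between-organization variation, because only two organizations contribute. Staff between-arm differences will be reported with intervals that account for organization, and their point estimates alone will not be used to size a larger study. The pilot will inform that study through recruitment and retention rates, youth outcome SDs and pre-post correlations.

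The following sentence, on feasibility-type information, can stay. How the larger study sets its target difference and ICC can be left to its own protocol.

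The cost is wording only: no new data, participants or procedures. The downside is that the larger study must justify its between-arm effect from another source.

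### Phase 2 randomises four organizations (2 v 2), but the Analytical Plan does not make the organization the unit of the between-arm tests; run on staff respondents, those tests would understate uncertainty

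*Combined protocol and SAP*

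**What the plan says.** All references are to the combined protocol and SAP.

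- **Design, Phase 2.** The randomised unit is the organization: "Four prevention organizations will be randomized either to include YE in prevention efforts (treatment) or not (control". The arms are to be matched where possible on location, population served or earlier YE involvement. The text does not say whether randomisation is within matched pairs.
- **Sample size, Phase 2.** "We plan to enroll up to 3 leaders/staff from each of four organizations", two per arm. Youth are enrolled only in treated organizations: "For each organization randomized to receive the intervention, we will also enroll up to 60 youth/YA participants".
- **Interventions and Interactions, Phase 2.** "However, only organizations randomized to treatment will include youth/YA participants". The between-arm data therefore come from the organizations and their staff.
- **Outcome Measure(s), Phase 2.** "For organizations, information collected from staff via surveys and interviews will include: perceived value added to prevention programming", followed by retention, reach, and the usefulness and effectiveness of YE. Of the youth outcomes it says: "These will serve as benchmarks that the YE intervention has the intended effect at the individual (psychosocial) level".
- **Analytical Plan.** Organization-level outcomes come first and youth outcomes second. The tests are given in one sentence: "Comparison between groups will be done using chi square tests for proportions, and t-tests or ANOVA procedures for continuous variables". Regression for predictors and further unspecified analysis are allowed. No unit of analysis, organization term, ICC or matching term appears. The data are also to supply effect sizes for powering a larger study.

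**The concern.** Staff in one organization rate the same programme in the same setting, so their answers may be alike for reasons unrelated to YE. With two organizations per arm, an ordinary difference between organizations can pass for a YE effect if each staff member counts as an independent observation. As written, an analyst could run a t-test on 12 respondents (10 df) or on four organization means (2 df), and both would fit the plan although their intervals differ about twofold.

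The organization-level comparison is the leading Phase 2 analysis, and its estimates feed the next study. With equal numbers of staff per organization, ignoring clustering does not bias the estimated difference; it makes that estimate look more precise than it is.

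There is a related gap. Some listed outcomes concern YE itself, and the Analytical Plan describes its lead example as the value that YE adds. The plan does not say how organizations assigned not to use YE would answer such items.

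**Working it through.** **Inputs from the documents.** Four organizations, two per arm; up to m = 3 staff each. The stated staff maximum reproduces: 3 × 1 (Phase 1) + 3 × 4 (Phase 2) = 15. Phase 2 therefore has at most 12 staff, 6 v 6.

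**Assumptions, not in the documents.** Normal outcome with total SD 1, two-sided 5% level, ICC from 0 to 0.5.

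**Step 1: standard error.** The difference between arm means, with two organizations per arm, has true SE = √(ICC + (1 − ICC)/m). A t-test on 12 staff estimates √((1 − 0.4 × ICC)/3) on average (root mean square, m = 3).

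| ICC | SE on 12 staff | True SE | Too small by |
|---|---|---|---|
| 0.05 | 0.571 | 0.606 | 6% |
| 0.1 | 0.566 | 0.632 | 11% |
| 0.2 | 0.554 | 0.683 | 19% |
| 0.5 | 0.516 | 0.816 | 37% |

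At ICC 0.1, for example, √(0.96/3) = 0.566 and √(0.1 + 0.9/3) = 0.632; the ratio √(0.32/0.40) is 0.894.

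**Step 2: type I error of the t-test** (400,000 simulated null trials per setting).

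| ICC | 12 staff (3 per organization) | 8 staff (2 per organization) | 12 staff, matching works* | Four organization means |
|---|---|---|---|---|
| 0 | 5.0% | 5.0% | – | 5.0% |
| 0.05 | 6.1% | 5.6% | 5.4% | 5.0% |
| 0.1 | 7.5% | 6.2% | 5.9% | 5.0% |
| 0.2 | 10.3% | 7.5% | 7.0% | 5.0% |
| 0.5 | 20.1% | 12.8% | 11.9% | 5.0% |

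*Assumes half of the between-organization variance is shared within matched pairs. The last column is without matching. With one staff member per organization there is no clustering and the error is 5%.

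**Step 3: chi-square on four organization values.** At full separation the 2 × 2 table is 2, 0 / 0, 2. Uncorrected χ² = 4 × (2 × 2 − 0 × 0)² / (2 × 2 × 2 × 2) = 4, so p = 0.046 on 1 df. Exact count: C(4,2) = 6 allocations, of which 2 are as extreme, so p = 2/6 = 0.33. If randomised within two pairs there are 2² = 4 allocations and the smallest two-sided p is 2/4 = 0.50. No exact randomisation test of this design can reach 5%.

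**Step 4: honest interval width** (95% half-width, t × true SE, 3 staff, ICC 0 to 0.1).

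- Organization means, 2 df: 4.303 × 0.577 = 2.48 to 4.303 × 0.632 = 2.72 SD.
- Paired, 1 df, no variance gain from matching: 12.706 × 0.577 = 7.34 to 12.706 × 0.632 = 8.04 SD.
- For comparison, 12 staff taken as independent, 10 df: 2.228 × 0.566 = 1.26 to 2.228 × 0.577 = 1.29 SD.

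At ICC 0, where clustering plays no part, the organization-level half-width is already 2.48 SD.

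**The case against.** **The plan may already intend analysis by organization.** It contrasts organization-level with individual-level outcomes, and one value per organization is a fair reading. A reader might infer that the plan tests staff as independent; it does not say so. But the wording describes the outcome, not the unit tested, and the data are surveys and interviews of individual staff. What stands is that the understatement is conditional. Retention and reach, if recorded once per organization, escape it altogether.

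**The effect is modest at plausible settings.** This largely stands. Three staff is a ceiling, the ICCs are assumed, and the 20% figure needs ICC 0.5, full enrolment and no gain from matching. At ICC 0 there is no error to correct.

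**It is a pilot, and further analysis is allowed where appropriate.** A reader might infer a wrong trial decision; with no alpha, power claim or decision rule, the documents do not support that. Still, the permissive sentence commits to no method, and inferential tests are planned.

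**The youth analysis.** A reader might infer that the pooled pre-post test is invalid because up to 60 youth share an organization. It is valid for the two treated organizations themselves. It would understate uncertainty only as a statement about organizations in general, a target that the plan never states. The sentence on benchmarks is limited to the individual, psychosocial level. What remains is a matter of reporting: two organizations and no control comparison.

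**Conclusion.** The omission is certain: the between-arm tests are tied to no unit, and organization is not accounted for. The harm is conditional. If staff are analysed as independent and ICC exceeds 0, the t-test error with 3 staff per organization is about 6–7.5% at ICC 0.05–0.1, 10% at 0.2 and 20% at 0.5, and it is lower with fewer staff or effective matching. If organization values are analysed, the t-test holds its level under normality, but an uncorrected chi-square on four units does not. The plan does not say whether a small-sample correction would be used.

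This should be fixed, because it affects how the leading comparison is read and how precise its effect sizes appear when the larger study is planned. It is not evidence of a biased estimate or a faulty trial decision. The main limit on what Phase 2 can show is the number of organizations, which analysis wording cannot change.

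**What to change.** In the Analytical Plan:

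1. Make the organization the unit of the between-arm comparison. Average staff responses to one value per organization, show all four values, and give the difference in organization means with a 2-df interval. If organizations are randomised within matched pairs, say so and show the two pair differences instead. Call the comparison descriptive, because the smallest exact two-sided p is 0.33 (0.50 if paired). Do not use chi-square tests on staff or on four units.
2. List the Phase 2 outcomes to be compared between arms, limited to those that control organizations can also report. Report items about YE itself in the treated arm only.
3. Report youth pre-post change for each treated organization, and state that it applies to those two organizations and has no control comparison.
4. Plan the larger study over a range of assumed ICCs.

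**Cost.** Wording only; recruitment, data collection and the intervention are unchanged. Between-arm half-widths rise from about 1.3 SD on 12 staff to about 2.5–2.7 SD on 2 df (ICC 0–0.1). Most of that is the price of having four organizations, not of clustering.
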